Sponsor	The sponsor is the party that commissions the organisation or performance of the research, for example a pharmaceutical company, academic hospital, scientific organisation or investigator. A party that provides funding for a study but does not commission it is not regarded as the sponsor, but referred to as a subsidising party.
SUSAR	Suspected Unexpected Serious Adverse Reaction
Wbp	Personal Data Protection Act (in Dutch: Wet Bescherming Persoonsgegevens)
WMO	Medical Research Involving Human Subjects Act (in Dutch: Wet Medisch-wetenschappelijk Onderzoek met Mensen)

SUMMARY

Rationale: Distal radius fracture (DRF) is a common injury that may lead to prolonged function restrictions, decreased range of motion, reduced grip strength and pain. These symptoms may be caused by physical changes due to the injury and/or by the 4-6 weeks immobilization that is part of the conservative treatment. However, it might also be that neural changes during the immobilization play an important role. Such changes might be prevented by motor imagery training during the immobilization period. So, when neural changes are prevented, this may lead to a better functional outcome.

Objective: The objective is to improve the functional outcome in distal radius fracture patients, specified as an increase in function, dexterity, grip strength, range of motion, and decrease of pain.

Study design: Parallel group randomized controlled trial, with a post-test only control group design. Patients in the experimental group perform motor imagery training during the immobilization period, in addition to the regular treatment. Patients in the control group receive regular treatment.

Study population: Female DRF-patients who are conservatively treated by a cast, aged 45-75 years. The fracture must be a low energy trauma caused by a fall. Patients with a score higher than 72 on the internal scale of the Vividness of Motor Imagery Questionnaire (VMIQ) are excluded, as well as patients with co-morbidities that might influence the wrist function, or motor imagery-ability, and patients with no understanding of Dutch language.

The patients are randomly allocated to the experimental or control group by restricted randomization to ensure equal group sizes. The randomization is conducted with use of PASW Statistics 18.

Intervention: Motor imagery training; 4 times a day 7 minutes of motor imagery training for 3 weeks (depending on duration of immobilization period).

Main study parameters/endpoints: The main study parameter is function. Secondary study parameters are dexterity, range of motion, grip strength, and pain.

Nature and extent of the burden and risks associated with participation, benefit and group relatedness: During the immobilization period, the patients in the experimental group are asked to perform motor imagery 4 times a day, whereby each session takes 7 minutes, so the time expenditure is 28 minutes a day. The outcome measures are determined twice in each group;

directly after cast removal and two weeks after cast removal. The measurements take place at the moments that the patients visit the hospital for a protocolized outpatient visit. Thus, the measurements do not require extra hospital visits.

Although there is only one study that examined the effectiveness of motor imagery training in peripheral injuries, many studies are conducted that demonstrate the effectiveness of motor imagery training in stroke patients, athletes and healthy subjects. Based on these studies, it is expected that motor imagery training will benefit recovery after a distal radius fracture. To our knowledge, there are no studies that identified the risks of motor imagery training. Since motor imagery training does not contain motion, it is highly unlikely that the intervention is harmful to the patients.

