3. STUDY DESIGN

The above hypothesis can be tested by conducting a parallel-group randomized controlled trial. The duration of this study is 5 weeks, depending on the length of the immobilization period. The patients will be measured during their visits to the hospital. The first measurement is conducted directly after removal of the cast. The second measurement is two weeks later, when the patients visit the hospital for their check-up appointment. A schematic view of the study is given below:

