6.7 Preparation and labeling of Investigational Medicinal Product

6.8 Drug accountability

7. METHODS

7.1 *Study parameters*

Based on literature about the outcome following a DRF (19-24), and experts' opinions, we decided to use 5 outcome measures. The main outcome measure is function. Other outcome measures used are the range of motion, grip strength, dexterity, and pain.

7.1.1 *Main study parameter/endpoint*

Research has shown that DRF-patients suffer more on long term from function restrictions than pain (15,16). Therefore, function is the main outcome measure. Function is measured using the Patient Rated Wrist/Hand Evaluation (PRWHE). This instrument is developed to measure disability during usual and specific activities, and it also documents pain and aesthetics. The PRWHE is derived from the PRWE and contains some extra questions about aesthetics. Because the PRWHE retains the originally validated questions, format and scoring system of the PRWE, it can be treated as the PRWE (59). A study that critically reviewed the available outcome assessment tools, showed that the PRWE is the most responsive instrument to measure outcome in DRF-patients (60). The PRWE is a self-rated questionnaire, and its mean completion time is 4 minutes (61). It consists of 15 questions, divided in 3 domains; pain, functional activities, and usual activities. The patients have to rate the severity of their pain or disability in different situations. The final score of the PRWE and PRWHE lies between 0-100, where 0 represents the best and 100 represents the worst outcome. The PRWE is found to be reliable and valid, and therefore provides a simple and quick method to measure patient-rated pain and disability (61).

7.1.2 *Secondary study parameters/endpoints*

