Grip strength is important for the execution of many occupational activities (72). It is measured using a hydraulic dynamometer, which is found to be reliable and valid (73). Research has shown that the position of the wrist can influence the maximal grip strength that can be applied. This is especially the case when the wrist is in ulnar or radial deviation, which is one of the deformities that is common after a DRF malunion (74). Therefore, it is useful to determine different grip strengths; grasp, tip pinch, key pinch, and three-jaw chuck pinch (72,73). The measurements will be conducted using a standardized protocol (73), to counter the effects of confounders. The mean of three trials has the highest test-retest reliability (73), and therefore, it is decided to measure the strength of each grip three times. To control for within-group variability, grip strength is measured on both hands.

Two dimensions of pain are measured using a Visual Analog Scale (VAS) (75); pain intensity and pain relief (76). This results in a score between 0 and 100, where 0 represents severe pain and low pain relief, and 100 represents no pain and large pain relief.

7.1.3 *Other study parameters*

Confounding factors that might influence the dependent variables are age, motor imagery ability, type of fracture, occupation, sport activities and involvement of their casted hand in activities. The patients will be asked for their occupation, sport activities and involvement of the

casted hand in activities. The confounding factors will be included in the statistical analysis as covariates to control for their influence.

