7.3 Study procedures

The study coordinator checks the diagnose lists of the department of Traumatology and Orthopedics, and identifies the female DRF-patients in the age of 45-75 years of age, who are conservatively treated. These patients will be randomly allocated to the experimental or control group. They receive an information letter and are asked to participate. When they decide to participate, they return an informed consent. When the patients visit the hospital for a medical check one week after initial treatment, the patients who are willing to participate are asked to fill out the Vividness of Motor Imagery Questionnaire. A score of 72 point or less on the internal scale (first person perspective) of the VMIQ, is one of the inclusion criteria. Therefore, this questionnaire is filled out before inclusion. The score on the VMIQ determines whether the patient can participate in the study or not. The patients who are allocated to the experimental group will receive information and instructions about the motor imagery training. To promote the imagery, the instructions are task-related:

- Flexion and extension: Patients are asked to imagine making a fist and imagine that they are slowly knocking on the table with their knuckles, making an exaggerated large movement.
- Adduction and abduction: Patients are asked to imagine that there are two dots drawn horizontally on the table in front of them. The hand lies between those dots, but there is still space between the hand and the dots. They are asked to imagine that they are trying to touch the right and the left dot with their little finger and thumb repeatedly, by only moving the palm of their hand.
- Pronation and supination: Patients are asked to imagine that they turn a key back and forth, by only using their hand and forearm.

In addition to these task-related instructions, the movements that have to be imagined are demonstrated by the study coordinator. Next, the patients are asked to repeat that movement once with their uninjured hand. The patients receive a letter that contains the instructions and are asked to repeat this protocol unsupervised at home. To promote their adherence to the motor imagery training, the patients in the experimental group will be contacted by phone on a weekly basis. To control for bias as a consequence of this extra attention, also the patients in the control group will be contacted by phone weekly.

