Three weeks later, which is 4 weeks after injury, the patients return to the hospital to remove the cast. At that moment, the first measurements will be performed. All tests will be performed by the study coordinator. Directly after cast removal, when they are still at the hospital, dexterity, the level of pain and pain relief, grip strength and range of motion will be determined. The PRWHE will be performed one day later by phone. Two weeks after cast removal, the second measurements will be conducted. Function, dexterity, the level of pain and pain relief, grip strength and range of motion will be measured.

The measurements will take place in the University Medical Center Groningen. The PRWHE and the VAS can be scored by the patients themselves, while the measurements with the SODA, goniometer and dynamometer will be conducted by the study coordinator. It is expected that the first measurements will take 30 minutes to complete, and the second measurements 35 minutes.

As explained in chapter 7.1, function is measured using the PRWHE. The PRWHE is a self-reporting instrument that determines the level of disability during specific and usual activities, and also contains some items to determine the level of pain and aesthetics (59). It takes on average 4 minutes to complete the questionnaire (61).

A digital goniometer is used to determine the active ROM. It is expected that the process of measuring ROM takes 6 minutes to complete.

Grip strength is measured using a hydraulic dynamometer (73). The strength of four different grips will be determined, according to the protocol as described by Mathiowetz et al. (1984). It is expected that the procedure to measure the grip strengths takes 4 minutes to measure both sides.

Dexterity is determined using the SODA. The SODA is a performance-based test, which measures the level of disability during activities of daily living (68). We expect that it takes 20 minutes to complete it. Instructions of the SODA will be given according to the protocol described by Van Lankveld et al. (1996).

The level of pain and the level of pain relief are determined using a VAS (75), a self-reporting scale. It is expected that it only will take a few seconds to complete it.

7.4 *Withdrawal of individual subjects*

The patients are free to withdraw from the study at any time, for any reason, and without consequences. Patients are withdrawn when the study coordinator thinks that participation by a

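### No pain or function score is taken before training, so a difference in symptom severity between the arms at entry could be neither shown nor directly adjusted for

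*Combined protocol and SAP*

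**What the plan says.** The Summary describes a "Parallel group randomized controlled trial, with a post-test only control group design". It places the outcome measurements "directly after cast removal and two weeks after cast removal". Section 3 agrees: "The first measurement is conducted directly after removal of the cast". Section 7.3 puts cast removal three weeks after the one-week visit and adds "At that moment, the first measurements will be performed", with the PRWHE following a day later by phone.

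Section 7.3 also describes the earlier contact. At the medical check one week after initial treatment, "the patients who are willing to participate are asked to fill out the Vividness of Motor Imagery Questionnaire". This covers both arms and comes before the training instructions: "Therefore, this questionnaire is filled out before inclusion". The VMIQ measures imagery ability and decides eligibility. It is not an outcome.

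On covariates, 7.1.3 states "Confounding factors that might influence the dependent variables are age, motor imagery ability, type of fracture, occupation, sport activities" and adds use of the casted hand. Section 9.1 describes patients on these potential confounders. Section 7.2 also plans an equal distribution of fracture type.

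Section 7.2 allocates patients before consent, with different information for each arm, and reports response rates of 35% (experimental) and 62% (control). Neither patients nor the researcher are blinded.

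**The concern.** Both PRWHE scores follow the training period. Section 10.4 expects experimental patients to be better off already when the cast comes off, so T1 may carry treatment effect. Adjusting for it, or treating it as the starting level, could remove part of what the trial is looking for.

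In a trial that randomises after consent, lacking an outcome baseline costs precision and little else. Here the groups analysed are those who agreed after receiving an arm-specific letter. One letter asks for 28 minutes of training a day and the other does not. If willingness to train is related to pain or disability, the arms can differ in severity at entry for reasons other than chance. The plan collects no pain or function data that could reveal this or adjust for it directly.

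**Working it through.** **Inputs from the documents.** PRWHE SD 26.13, target difference 5.3 points, total 52 (4.4); equal groups, hence 26 per arm, and consent rates of 35% and 62% (7.2); two-sided 5% level (9.3). **Assumed:** r, the correlation between a one-week score and the T2 PRWHE, which the documents do not give.

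**1. The plan's own sample size.** For the within-between interaction with f = 0.20, two measurements, and correlation 0.5 and epsilon 1 (assumed to be the software defaults), the noncentrality is f² × N × 2/(1 − 0.5). At N = 52 this is 0.04 × 52 × 2/0.5 = 8.32, giving power 0.807; N = 50 gives 0.791. The stated 52 is reproduced. It uses no baseline score, so this point does not alter it.

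**2. Selection after allocation.** To obtain 26 per arm, 26/0.35 = 74.3 (about 75) experimental and 26/0.62 = 41.9 (about 42) control patients must be invited. So about 49 experimental invitees and 16 controls do not take part.

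**3. What an imbalance would do.** An entry imbalance of b SDs shifts the T2 difference by b × r × 26.13. For b = 0.2 this is 1.6 points at r = 0.3 and 2.6 points at r = 0.5, against a target of 5.3. Chance alone gives a standard error of √(2/26) = 0.277 SD for the entry difference, so an imbalance above 0.2 SD has probability 47%. Chance imbalance is already allowed for in the standard error of the comparison. Imbalance from selective consent is not.

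**4. Precision at T2.** Unadjusted SE = 26.13 × √(2/26) = 7.25. Adjusted SE = 7.25 × √(1 − r²). Equivalent sample gain is 1/(1 − r²) − 1 if everyone is measured, and 1/(1 − r²/2) − 1 if half are already enrolled without a score (assumption). The difference detectable with 80% power is (1.960 + 0.842) × SE.

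| r | SE (points) | Gain, all measured | Gain, half measured | Detectable difference | Power for 5.3 points |
|---|---|---|---|---|---|
| 0 | 7.25 | – | – | 20.3 | 0.110 |
| 0.2 | 7.10 | 4% | 2% | 19.9 | 0.112 |
| 0.3 | 6.91 | 10% | 5% | 19.4 | 0.116 |
| 0.5 | 6.28 | 33% | 14% | 17.6 | 0.132 |

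SE, detectable difference and power assume that everyone is measured. If 80% are already enrolled, the gain at r = 0.5 is 1/(1 − 0.25 × 0.2) − 1 = 5%.

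**5. Group-by-time interaction.** With two time points this compares T2 − T1 between the arms. If the one-week score correlates equally with T1 and T2 and their SDs are equal, its covariance with T2 − T1 is zero, and adjusting for it adds no precision to that test.

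**The case against.** The post-test-only design is declared, and randomisation supports a comparison without an outcome baseline. A reader might infer that the planned comparison is therefore invalid, or that the arms do differ in severity. The documents support neither: they report different consent rates but nothing on severity by arm. Nor is the analysis without covariates. Age, imagery ability, fracture type, occupation, sport and use of the casted hand are planned, and some may share prognostic information with a symptom score. The gains above are measured against an unadjusted comparison, so they overstate the net benefit to that extent.

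A PRWHE scored with the wrist in plaster may also be a weak predictor. Its activity items may bunch near the worst score, which would make r low. This is inference, as the documents hold no data on it, but it favours the pain items and the VAS.

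The score would be given after patients had read their arm-specific letter, so knowledge of allocation could colour it. Finally, 7.2 refers to 2.5 years of inclusion, so an unknown share of patients is already enrolled without a score.

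All of this stands, and it limits the benefit. It does not remove the gap: none of the planned covariates measures pain or disability before training, T1 cannot fill that role, and consent follows allocation.

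**Conclusion.** The point holds as a cheap improvement to the design. Its main basis is that the arms cannot be compared on symptoms at entry when consent differs by arm (35% versus 62%). Precision is the secondary reason. With everyone measured, the equivalent sample gain is 4% to 33% for r from 0.2 to 0.5, before overlap with the planned covariates. If half are already enrolled, it is about 5% at r = 0.3 and 14% at r = 0.5. Both r and the enrolled share are assumptions.

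A reader might infer that a baseline would rescue the trial's power. It would not: power for 5.3 points at T2 stays near 0.11 to 0.13, and the interaction test gains little or nothing. The contrast between that power and the 0.807 reproduced for the interaction is a separate sample-size question.

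**What to change.** - **Section 7.3:** at the one-week visit, in both arms and before any instruction, add VAS pain intensity and the self-completed PRWHE, or at least its pain items.
- **Section 9.3:** enter the one-week PRWHE score (or pain-item score, if only that is collected) as a covariate for the PRWHE, and the one-week VAS for pain, in the between-group comparisons at T1 and T2. Keep the covariates already planned. For patients enrolled before the change, set the missing score to the overall mean and add a missing indicator.
- **Section 9.1:** tabulate the one-week scores by arm, with the number of patients measured.

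The cost is an amendment and a few minutes at an existing visit. Section 7.1.1 says "The PRWE is a self-rated questionnaire, and its mean completion time is 4 minutes", and 7.3 expects the VAS to take seconds. Earlier patients will have no value. Because scores follow the arm-specific letter, the tabulation is an indicative check on the arms at entry and should be described as such.

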1. INTRODUCTION AND RATIONALE

1.1 *Relevance*

Distal radius fracture (DRF) is a common injury (1-5). In adults, the incidence rates for women are 368 per 100.000 persons per year, and for men 90 per 100.000 persons per year. (6).

Incidence rates are higher with increasing age, due to a higher tendency to falls. They are also higher in women compared to men, mainly due to osteoporosis (4).

A DRF can be treated either conservatively or surgically by different methods, immobilization by plaster cast is one of it. Most DRF's are treated conservatively, especially when the fracture is not impacted, is reducible, stable and the joint surface is not involved. Mostly, a plaster cast is applied for 4-6 weeks to avoid the loss of fracture reduction (7). This immobilization period causes physical changes like muscle atrophy (8-10) and contractures (11,12).

Usually, DRF-patients are advised to do exercises after the immobilization period to prevent further complications associated with the fracture or the treatment, optimize functional recovery, and to be able to achieve normal functioning in activities of daily living again (13,14).

However, research has shown that many DRF-patients suffer from pain, disability, decreased range of motion and reduced grip strength, shortly, but also long after the injury (15-18). It is reported that even after a few years, ranging from 2 to 26 years after injury, DRF-patients still had function restrictions (18). Also when DRF-patients follow a physiotherapy course or a home exercise program, 45-95% still have some form of pain and reduced function (15-17), which are most profound on work related and recreational activities (15,16). The fact that physiotherapy does not seem to improve the functional outcome (19-24), can partly be explained by high energy traumas and osteoporotic fractures (25). Such traumas mostly involve anatomical deformations which are related to poor functional outcome (26). However, in other cases with low energy trauma, it is likely that other factors relate to the functional outcome too.

Limb disuse and immobilization can cause neural changes, such as reorganization in the sensorimotor cortex and cerebellum, and changes in excitability of the motor cortex (27-29).

When this happens during immobilization after DRF, it will partly be responsible for complaints as clumsiness and functional restrictions that DRF-patients report (30-33). Motor imagery during the immobilization period might prevent (part of) these neural changes. Motor imagery is the mental process by which a subject performs an action mentally, and it has been found that during motor imagery, overlapping cortical areas are activated as during real execution of the same movement (34-37). So, motor imagery training of wrist movements during the

immobilization period following a DRF might prevent neural changes caused by limb disuse, which might underlie part of the remaining problems of these patients. Therefore, the aim of this study is to determine whether motor imagery training during the immobilization period following a DRF might prevent functional decay as result of limb disuse on short term. This might lead faster to a better functional outcome.

This study contributes to the existing knowledge of the effectiveness of motor imagery training, and it provides new knowledge about the effect of motor imagery during immobilization after peripheral injury. Furthermore, when it is found that motor imagery during immobilization following a DRF is beneficial, a simple and cheap rehabilitation method is found that can be used in addition to existing rehabilitation methods in treating DRF. When DRF-patients recover more quickly, health costs will decrease, and patients will be able to return to work and to normal daily activities earlier. This is an important aspect, because it is found that work related activities and recreational activities are affected most and the most prolonged (15,16).

